Appendix 7.1 Informed consent, Denmark

This amendment replaces Appendix 7 in the above-mentioned protocol.

Description: New legislation on informed consent in Denmark.

Amendment 2 (December 2016)

Appendix 7.2 Informed consent, Denmark

This amendment replaces Appendix 7.1 in the above-mentioned protocol.

Description: New legislation on informed consent in Denmark.

Amendment 3 (June 2017)

Appendix 3.1 Charter for the independent Data Monitoring and Safety Committee (DMSC)

This amendment replaces Appendix 3 in the above-mentioned protocol.

Description: Cancellation of the second interim analysis (2500/3350 included patients).

Due to the inclusion rate the SUP-ICU trial Steering Committee, in full agreement with the DMSC, has decided to cancel the second interim analysis as the results (incl. 90-day follow-up) would be available only after the inclusion of the last trial patient.

The statement paper from the DMSC following the first interim analysis (1675/3350 included patients) supports this decision. The decision has been approved by relevant Danish authorities.

Stress Ulcer Prophylaxis in the Intensive Care Unit (SUP-ICU) trial: detailed statistical analysis plan

Comprehensive details of the SUP-ICU trial has been published elsewhere.¹ This statistical analysis plan was prepared before randomisation of patients and data collection in the SUP-ICU trial was completed. The analysis plan was approved by the SUP-ICU Steering Committee on September 22, 2016. Analysis of data for the primary publication will be conducted according to this plan.

Randomisation

Thirty-one sites in Denmark, Finland, the Netherlands, Switzerland and Norway are currently screening and randomising patients in the SUP-ICU trial. Some additional, 5-10 ICUs from the United Kingdom, Italy and Denmark are expected to participate. Copenhagen Trial Unit (CTU)²¹ is responsible for centralised and web-based 1:1 randomisation according to a computer-generated allocation sequence list, with two stratification variables (site and active hematologic cancer), and varying block size.

Blinding

The allocated trial medication will be masked to clinical staff caring for the patient, to the patient, investigators and outcome assessors. The statistical analysis of the trial will be blinded with the intervention groups coded as, e.g., X and Y. Based on this blinded analysis two conclusions will be drawn: one assuming X is the experimental group and Y is the control group, and another assuming the opposite. Two abstracts will be written and accepted by the SUP-ICU Steering Committee. After this, the intervention groups will be unmasked.

Sample size

Because of the widespread use of SUP, no reliable control group for sample size estimation is available and producing reliable sample size estimations according to anticipated effects on GI bleeding is difficult.¹ As a consequence it has been necessary to calculate sample size estimations given that something may change if we withhold PPI until GI bleeding actually happens. Assuming a baseline 90-day mortality of 25%,² $\alpha=0.05$ (two-sided), and $\beta=0.1$, 3350 patients (2 x 1675) will be needed to show a 20% relative risk reduction (RRR) or increase (RRI) corresponding to a 5% absolute risk reduction or increase in the primary outcome measure. Trial Sequential Analysis^{22,23} of existing trials (n=16) has showed that 35% (1584 patients) of the required information size to

detect or reject a 20% RRR or RRI corresponding to 4575 patients has been accrued.⁸

Consequently, there is at least an information gap of around 3000 patients taking a 20% RRR in mortality as a clinically relevant effect size.

Outcome measures

Primary outcome

The primary outcome measure is all-cause mortality within 90 days after randomisation.

Secondary outcomes

1. Proportion of patients with one or more episodes of clinically important GI bleeding, pneumonia, *Clostridium difficile* infection or myocardial ischemia. The events are defined in appendix 1
2. Proportion of patients with one or more episodes of clinically important GI bleeding
3. Proportion of patients with one or more infectious adverse events (pneumonia or *Clostridium difficile* infections)
4. All-cause mortality within 1 year after randomisation
5. Percentage of days alive without use of life support (mechanical ventilation, circulatory support or renal replacement therapy) in the 90-day period
6. The number of patients with one or more serious adverse reactions (SARs) (defined in appendix 2)
7. A health economic analysis will be performed. The analytic details will be based on the result of the trial and specified prior to the analysis.

Pre-planned subgroup analyses

The primary outcome measure will be compared in the following pre-specified subgroups (definitions provided in appendix 2)

1. Shock at randomisation (y/n) (a hypothesised increased intervention effect in patients with shock at randomisation)
2. Mechanical ventilation at randomisation (y/n) (a hypothesised increased intervention effect in patients mechanically ventilated at randomisation)
3. Coagulopathy at randomisation or history of coagulopathy (y/n) (a hypothesised increased intervention effect in patients with acute coagulopathy/history of coagulopathy at randomisation)
4. History of liver disease (y/n) (a hypothesised increased intervention effect in patients with history of liver disease at randomisation)

5. Type of ICU admission (medical/surgical) (a hypothesised increased intervention effect in surgical patients)
6. Simplified acute physiology score (SAPS) II > 53 points (y/n) (a hypothesised increased intervention effect in the patients with higher SAPS II at randomisation)

Registered variables

Baseline variables

- Shock (continuous infusion with vasopressors or inotropes, systolic blood pressure < 90 mmHg, mean arterial blood pressure < 70 mmHg or lactate > 4 mmol/l)
- Acute or chronic intermittent or continuous renal replacement therapy
- Invasive mechanically ventilation which is expected to last > 24 hours.
- Coagulopathy (platelets < 50 x 10⁹/l or international normalized ratio (INR) > 1.5 or prothrombin time (PT) > 20 seconds) documented within the last 24 hours
- Ongoing treatment with anticoagulant drugs (prophylactic doses excluded)
- History of coagulopathy (platelets < 50 x 10⁹/l or INR > 1.5 or PT > 20 seconds within 6 months prior to hospital admission)
- History of chronic liver disease (portal hypertension, cirrhosis proven by biopsy, computed tomography (CT) scan or ultrasound, history of variceal bleeding or hepatic encephalopathy in the past medical history)
- Sex
- Age at randomisation/date of birth
- Date of admission to hospital and date and time of admission to ICU
- Elective or emergency surgery during current hospitalization (y/n)
- Treatment of suspected or confirmed *Clostridium difficile* infection during current hospital admission (y/n)
- Treatment with nonsteroidal anti-inflammatory drugs (NSAID) or acetylsalicylic acid at hospital admission (y/n)
- Treatment with anticoagulants at hospital admission (prophylaxis not included) (y/n)
- Intravenous thrombolysis within the previous 3 days (y/n)
- Co-morbidities (defined in appendix 1):
 - history of chronic lung disease
 - history of myocardial ischemia
 - history of severe chronic heart failure (NYHA 3-4)
 - history of chronic renal failure in the last year prior to hospital admission

- treatment with at least 0.3 mg/kg/day of prednisolone equivalent for at least one month in the 6 month prior to ICU admission
- active hematologic cancer:
 - metastatic carcinoma
 - acquired immune deficiency syndrome (AIDS)
- Values for SAPS II and severity organ failure assessment (SOFA) scoring 24 hours prior to randomisation.

Daily during ICU admission

- Delivery of trial medication (y/n)
- Open label treatment with PPI/histamine-2-receptor antagonists (y/n)
- Invasive or non-invasive mechanical ventilation (y/n)
- Circulatory support (infusion of vasopressor/inotropes) (y/n)
- Any form of renal replacement therapy (y/n)
- Onset of pneumonia on this day (y/n)
- Treatment with antibiotics (enteral vancomycin, intravenous or enteral metronidazole, or enteral fidaxomicin) for suspected or proven *Clostridium difficile* infection on this day (y/n)
- Acute myocardial ischemia on this day (y/n)
- Enteral feeding on this day (y/n)
- Number of units of red blood cells transfused
- Overt GI bleeding episodes (hematemesis, coffee ground emesis, melena, haematochezia or bloody nasogastric aspirate) (y/n)
- Serious adverse reactions (SARs) (y/n) (appendix 2)

Bleeding form (only for patients with overt bleeding)

- Data on clinically important GI bleeding:
 - A spontaneous drop of systolic blood pressure, mean arterial pressure or diastolic blood pressure of 20 mmHg or more
 - start of vasopressor or a 20% increase in vasopressor dose
 - decrease in haemoglobin of at least 2 g/dl (1.24 mmol/l)
 - transfusion of 2 units of packed red blood cells or more
- Origin of GI bleeding confirmed (y/n)
- Verification of ulcer/gastritis/esophageal varices (y/n)
- Haemostasis achieved/attempted by endoscopy/open surgery/coiling (y/n)

Follow-up 90 days and 1 year after randomisation

- Death (y/n, if yes, date of death)

Missing data

If more than 5% of the observations are missing for any specific analysis that analysis will be conducted both as complete-case and using multiple-imputation based on chained equations. All variables in the specific analysis will be included in the multiple imputation as well as stratification variables (site and presence of haematological cancer), age, SOFA score at baseline, type of admission (medical, elective surgery or emergency surgery), SAPS II at baseline, renal replacement therapy at baseline, mechanical ventilation at baseline, shock at baseline, proportion of patients with clinically important GI bleeding, proportion of patients with one or more episodes of serious adverse events (pneumonia, *Clostridium difficile* infection and myocardial ischemia), and 90-day mortality.

If multiple imputation is used, the primary result of the trial will be based on these data. A 'best-worst, worst-best case' scenario will be used as a sensitivity analysis to assess the potential impact of any pattern of missingness including that the data are missing not at random (MNAR criterion) for the trial results. In the 'best-worst-case' scenario it is assumed that all patients lost to follow-up in the experimental group have had a beneficial outcome (e.g. have survived) and all those with missing outcomes in the control group have had a harmful outcome (e.g. have not survived). Conversely, in the 'worst-best-case' scenario, it is assumed that all patients who were lost to follow up in the experimental group have had a harmful outcome; and that all those lost to follow-up in the control group have had a beneficial outcome.

The unadjusted, non-imputed analysis will also be presented.

General analytic principles

1. All main analyses will compare the two intervention groups in the intention-to-treat (ITT) population.²⁴⁻²⁶

The ITT population will be all patients randomised except:

- patients withdrawing consent for the use of data
- patients who were erroneously randomised AND who did not receive the trial intervention.²⁷

The conclusion of the trial will be based on the ITT analysis

2. In all analyses, a maximum level of 5% (two-sided) type 1 error will be regarded as statistically significant
3. Test-of-interaction will be applied for all subgroup analyses (logistic regression)

Statistical analyses

Trial profile

The flow of trial participants will be displayed in a Consolidated Standards of Reporting Trials (CONSORT) diagram. The number of participants fulfilling the inclusion criteria, the number of excluded participants and reasons for exclusion, and the number of participants included in the final analyses will be presented.

Primary outcome measure

The primary analysis will be a logistic regression analysis adjusted for stratification variables (site and presence of haematological cancer, y/n) of the ITT population. Results will be presented as odds ratios and relative risk ratios (relative risk ratios computed from odds ratios with covariates set to mean values for numeric covariates and the largest group for categorical).

The secondary analysis will be a multiple logistic regression analysis of the ITT population adjusted for stratification variables and additionally differences in potential confounders: age, SOFA score at baseline, and type of admission (medical, elective surgery or emergency surgery). Intervention group and the stratification variable haematological cancer are regarded as fixed effects and trial site is regarded as random effects in the model. Furthermore, frequencies and percentages per group will be reported and an unadjusted Chi-square test for differences in the primary outcome will be provided.

Pre-defined subgroup analyses (see former section) of the ITT population will be conducted using logistic regression analysis adjusted for stratification variables.

A sensitivity analysis of the primary outcome measure including the per-protocol population will be conducted. The per-protocol population will be all randomised patients except those having one or more protocol violations defined as:

- Patients who did not receive the allocated trial intervention at all
- Patients who did not receive the trial intervention for at least two days in a row
- Patients who received treatment (open label) with PPI or histamine-2-receptor antagonists except for those receiving it according to the protocol (i.e. occurrence of GI bleeding after randomisation).
- Patients who withdrew from trial intervention, but consented to the use of data
- Monitoring revealed that one or more in- or exclusion criteria were violated

Secondary outcome measures

The secondary outcomes will only be analysed in the ITT population. The primary analysis of the binary secondary outcome measures will be a logistic regression analysis adjusted for the stratification variables (site and presence of haematological cancer). Results will be presented as odds ratios and relative risk ratios.

Furthermore, frequencies and percentages per group will be reported and an unadjusted Chi-square test for differences in the primary outcome will be provided.

The primary analysis of rate data ('Percentage of days alive without life support in the 90-day period') will be a generalized linear model (initially Poisson distribution, alternatively negative binomial).²⁸ If the assumptions for Poisson distribution or negative binomial distribution are not met, data will be analysed using the non-parametric Van Elteren test adjusted for site, but no other variables.²⁹

The secondary analysis of binary secondary outcomes will be a multiple logistic regression analysis additionally adjusted for differences in potential confounders: age, SOFA score at baseline, and type of admission (medical, elective surgery or emergency surgery).

Interim analysis

The Data Monitoring and Safety Committee (DMSC) will perform two formal interim analyses when 90-day follow-up data of 1650 (approximately 50% of sample size estimation) and 2500 (approximately 75% of sample size estimation) patients have been obtained. For the two intervention groups, the DMSC will evaluate data on:

The primary outcome measure

Mortality 90 days after randomisation of each patient ("landmark mortality").

The secondary outcome measures

- Proportion of patients with one or more of the following adverse events: clinically important GI bleeding, pneumonia, *Clostridium difficile* infection, or acute myocardial ischemia
- Proportion of patients with clinically important GI bleeding
- The occurrence of SARs in the ICU

The DMSC will be provided with the following masked (as group 0 and 1) data from the coordinating centre as:

- Number of patients randomised
- Number of patients randomised per intervention group
- Number of patients stratified per stratification variable per intervention group
- Number of events, according to the outcomes, in the two groups

Based on evaluation of these outcomes, the DMSC will decide if they want further data from the coordinating centre and when to perform the next analysis of the data. Additionally, the DMSC will yearly be informed about SARs occurring in the two groups of the trial. The interim analyses will be performed by an independent statistician selected by the members of the DMSC. The DMSC can, at any time during the trial, request the distribution of events, including outcome measures and SARs according to intervention groups. Further, the DMSC can request unblinding of the interventions. The DMSC may recommend pausing or stopping the trial if group-difference in the primary outcome measure, SARs or Suspected Unexpected Serious Adverse Events (SUSARs) are found in the interim analyses with statistical significance levels adjusted according to the LanDeMets group sequential monitoring boundaries based on O'Brien Fleming alpha-spending function.³⁰ If an analysis of the interim data from 1650 or 2500 patients fulfils the LanDeMets stopping criterion the inclusion of further patients will be paused and an analysis including patients randomised during the analysis period will be performed. If this second analysis also fulfils the LanDeMets stopping criterion according to the group sequential monitoring boundaries the Steering Committee may stop the trial.²⁶ Furthermore, the DMSC can recommend pausing or stopping the trial if continued conduct of the trial clearly compromises participant safety. However, stopping for futility to show an intervention effect of 15% RRR or RRI will not occur, as intervention effects less than 15% RRR or RRI in all-cause mortality may be clinically relevant as well.

Ethical approval and Consent to participate

The SUP-ICU trial has been registered on www.clinicaltrials.gov (NCT02467621), the trial is approved by the Danish Health and Medicine Agency (2015030166), the Committees on Health Research Ethics in the Capital Region of Denmark (H-15003141) and by the Danish Data Protection Agency (RH-2015-3203695).

Additionally, the trial is approved by the following ethical committees:

Norway: Regionale Komiteer for Medisinsk og Helsefaglig Forskningsetikk (2015/1490/REK vest)

Finland: Tutkimuseettinen toimikunta (372/2015)

The Netherlands: Medisch Ethische Toetsingscommissie (M15.182376)

Switzerland: Kantonale Ethikkommission Bern (205/15)

Consent will be obtained according to national law. The consenting party will be provided with written and oral information about the trial, so he/she is able to make an informed decision about participation in the trial. Written information and the consent form will be subjected to review and approval by the ethical committee system according to national law in all participating countries. The consenting party can at any time, without further explanation, withdraw consent.

Data sharing statement

The final dataset used for analysis will be shared through an open access data repository

LIST OF ABBREVIATIONS

AIDS	Acquired immune deficiency syndrome
CONSORT	Consolidated Standards of Reporting Trials
CTU	Copenhagen Trial Unit
DASAIM	Danish Society of Anaesthesiology and Intensive Care Medicine
DMSC	Data Monitoring and Safety Committee
GI	Gastrointestinal
ICU	Intensive care unit
INR	International normalized ratio
ITT	Intention-to-treat
NSAID	Nonsteroidal anti-inflammatory drugs
PPI	Proton pump inhibitor
PT	Prothrombin time
RRI	Relative risk increase
RRR	Relative risk reduction
SAPS	Simplified acute physiology score
SAR	Serious adverse reaction
SOFA	Severity organ failure assessment
SSAI	Scandinavian Society of Anaesthesia and Intensive Care Medicine
SUP	Stress ulcer prophylaxis
SUSAR	Severe unexpected serious adverse reaction

REFERENCES

1. [name], [name], Wetterslev J, Wise MP, Borthwick M, Bendel S, Pelosi P, Keus F, Guttormsen AB, Schefold JC, Møller MH. Stress ulcer prophylaxis with a proton pump inhibitor versus placebo in critically ill patients (SUP-ICU trial): study protocol for a randomised controlled trial. *Trials* 2016 ; 17: 205.
2. [name], [name], Wetterslev J, Wise MP, Borthwick M, Bendel S, McArthur C, Cook D, Nielsen N, Pelosi P, Keus F, Guttormsen AB, Moller AD, Møller MH. Prevalence and outcome of gastrointestinal bleeding and use of acid suppressants in acutely ill adult intensive care patients. *Intensive Care Med* 2015 ; 41: 833–45.

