7.2 Secondary outcomes

- Proportion of patients with one or more of the following adverse events: clinically important GI bleeding, pneumonia, CDI, or acute myocardial ischemia in the ICU
- Proportion of patients with clinically important GI bleeding in the ICU
- Proportion of patients with one or more infectious adverse events (pneumonia or CDI) in the ICU
- 1-year “landmark” mortality post-randomisation
- Days alive without the use of mechanical ventilation, renal replacement therapy or circulatory support in the 90-day period
- Number of SARs as defined in *appendix 4*
- A health economic analysis will be performed. The analytic details will be based on the result of the trial and specified (cost-benefit vs cost-minimisation analyses)

The specific elements of the composite outcomes will be reported in supplementary material to the primary publication.

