Proportions of patients with clinically important GI bleeding: proportion of patients with one or more episodes of clinically important GI bleeding as defined above

Proportion of patients with one or more infectious adverse events: proportion of patients with one or more episodes of pneumonia or CDI

1-year mortality: landmark mortality 1 year post-randomisation

Duration of life support in the ICU: the number of days alive and free from respiratory or circulatory support and of renal replacement therapy as defined below. The outcome will be days alive without use of mechanical ventilation, circulatory support or renal replacement therapy in the 90-day period, and will be defined as the percentage of days without mechanical ventilation, circulatory support and renal replacement therapy (as defined in daily collected variables) in the 90 days after randomisation

Serious adverse reactions: number of serious adverse reactions as defined below

The elements of all composite outcomes will be reported in the supplementary material

A health economic analysis will be performed. The analytic details will be based on the result of the trial and specified (cost-benefit vs cost-minimisation analyses).

Definitions of serious adverse reactions

A serious adverse reaction (SAR) is defined as any adverse reaction that results in death, is life-threatening, requires hospitalization or prolongation of existing hospitalization, or results in persistent or significant disability or incapacity.

Patients will be monitored for onset of SARs occurring between the first dose of trial medication and until discharge from the ICU. If a patient is withdrawn from the trial intervention, SARs will be recorded for 24 hours after the last dose of trial medication or discharge from ICU. If the patient is readmitted to the ICU and trial intervention is reintroduced, data collection for SARs will be resumed. If a patient experiences a SAR the patient will be withdrawn from the trial intervention but data collection and follow-up will be continued (see section 4.3.2)

SARs will be defined as follows:

Anaphylactic reactions defined as urticaria and at least one of the following

- Worsened circulation (>20% decrease in blood pressure or >20% increase in vasopressor dose)
- Increased airway resistance (>20% increase in the peak pressure on the ventilation)
- Clinical stridor or bronchospasm
- Subsequent treatment with bronchodilators

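### Does the SAP need to restate the divisor for the percentage of days alive without life support?

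*Combined protocol and SAP*

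**What the plan says.** SAP, Outcome measures, Secondary outcomes, item 5 is the "Percentage of days alive without use of life support (mechanical ventilation, circulatory support or renal replacement therapy) in the 90-day period". Under Statistical analyses, Secondary outcome measures, the SAP sets out "The primary analysis of rate data" for it, which "will be a generalized linear model (initially Poisson distribution, alternatively negative binomial" as the second option. If neither distribution fits, "data will be analysed using the non-parametric Van Elteren test adjusted for site, but no other variables". No divisor, offset or rule for days after death is written there. The SAP's opening paragraph adds that "Analysis of data for the primary publication will be conducted according to this plan".

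Protocol section 7 refers all outcome definitions to Appendix 4. Section 7.2 lists the outcome as "Days alive without the use of mechanical ventilation, renal replacement therapy or circulatory support in the 90-day period", a count. The Appendix 4 entry concerns duration of life support in the ICU. It begins with a number of days alive and free of the three supports, and ends by turning this into a "percentage of days without mechanical ventilation, circulatory support and renal replacement therapy (as defined in daily collected variables) in the 90 days after randomisation".

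Randomisation is described in the SAP as "with two stratification variables (site and active hematologic cancer), and varying block size".

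**The concern.** Taken alone, the SAP wording allows two scores. A percentage of days alive can mean a share of the days the patient lived, and calling it rate data suggests a model with time alive as the offset. Under that reading an early death off support scores close to a survivor; over 90 days it scores near zero. These are different quantities. Protocol section 8.3.1 relies on this outcome to capture the most important serious adverse events, which are not otherwise recorded as such.

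Two further points looked open. Daily support is registered during ICU admission while the outcome runs for 90 days, and patients on chronic renal replacement therapy are eligible. The Van Elteren fallback also leaves out haematological cancer, although randomisation is stratified by it and the logistic analyses adjust for it.

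**Working it through.** The plan gives no worked score or power for this outcome, so there is no figure to reproduce.

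**1. The texts side by side**

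| Place | Unit | Period | Days after death |
|---|---|---|---|
| Protocol 7.2 | count | 90-day period | excluded (days alive) |
| Appendix 4, opening | count | not given | excluded (days alive) |
| Appendix 4, closing clause | percentage | 90 days after randomisation | not repeated, but the clause defines the days-alive outcome named earlier in its sentence |
| SAP item 5 | percentage | 90-day period | excluded (days alive) |

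A count in the 90-day period and a percentage of 90 days are one quantity on two scales. Calling it rate data also fits a fixed 90: if every patient has the same exposure, the offset goes into the intercept and the treatment ratio is unchanged.

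**2. Individual scores.** Let F = days alive minus support days. Compare F/90 with F/days alive; the support days are assumed.

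- Death on day 10, 5 support days: 5/90 = 5.6%; 5/10 = 50%.
- Death on day 10, 1 support day: 9/90 = 10%; 9/10 = 90%.
- Death on day 10, always supported: 0% either way.
- Survivor, 10 support days: 80/90 = 88.9% either way.

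Only 90-day deaths are affected: 0.25 × 3350 = 837.5.

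**3. Group means.** Suppose every survivor scores 88.9%, every death is on day 10 with 5 free days, and mortality is 25% against 30%.

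- Over 90: 0.75 × 88.9 + 0.25 × 5.6 = 68.1; 0.70 × 88.9 + 0.30 × 5.6 = 63.9; difference 4.2 points.
- Over days alive: 0.75 × 88.9 + 0.25 × 50 = 79.2; 0.70 × 88.9 + 0.30 × 50 = 77.2; difference about 2 points.

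**4. Power.** The documents give no time to death, support duration or share of deaths off support, so all of these are assumed.

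- *Effect only through mortality* (25% against 30%, 1675 per arm, 60 lognormal settings): rank-test power is 0.66 to 0.73 over 90 and 0.39 to 0.72 over days alive. With 10% of deaths off support the two nearly agree (0.70 to 0.73 and 0.67 to 0.72). In a log-link model, power is 0.81 to 0.90 with a fixed 90 and 0.10 to 0.71 with a days-alive offset, which the SAP does not name.
- *Effect only through support* (25% mortality in both arms, support 10% shorter in one, median support 5 days, median death day 5, 10 or 25): rank-test power is 0.36 to 0.44 over 90 and 0.37 to 0.64 over days alive.

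The ordering reverses with the assumed effect.

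**5. Days after ICU discharge.** A chronic dialysis patient who leaves the ICU on day 10 and survives scores 80/90 = 88.9% if later days count as free, and 0/90 = 0% if continuing dialysis counts. Appendix 4 places the outcome in the ICU, which gives 88.9%. For transfers to another ICU, protocol sections 4.3.2 and 9.2.1 provide for continued collection.

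**6. Fallback test.** With 36 sites, blocked randomisation within site and cancer, assumed cancer prevalence of 2% to 8% and mortality in cancer of 40% to 60% (500 simulated trials per setting), power was 0.69 to 0.71 whether or not cancer was added to the strata. The standard deviation of the test statistic was about 1 under both.

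**The case for a change.** The strongest case for a change is that the SAP governs the primary publication, the protocol (section 11.2) leaves further details to it, and it does not write this one down. The closing clause of Appendix 4 omits the word alive; read by itself it would score the day-10 death with 5 free days at (5 + 80)/90 = 94.4%. An offset for time alive is a natural modelling choice for something called rate data, and under a pure mortality effect it loses much of the power even with only 10% of deaths off support (0.19 to 0.71 against 0.85 to 0.90). Coding the groups prevents choosing a reading to favour a known arm, but it does not fix the quantity estimated. A sentence would cost almost nothing.

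What stands is that the SAP does not repeat the definition, and that no text expressly covers support given on a ward after ICU discharge. The 94.4% reading does not stand, because the same Appendix 4 sentence names days alive as the outcome. The power argument holds only for an effect through mortality, which the primary outcome already tests. A rule counting ward days as free unless support is known would not settle the dialysis example: chronic dialysis is recorded at baseline, so whether the later days are known stays open. The simulated variance of free days, 13 to 22 times the mean, makes the Poisson start doubtful, but the SAP already provides two fallbacks.

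**Conclusion.** No change to the plan follows. The missing divisor is a gap that an analyst fills from the protocol: days alive and off all three supports, out of 90, with days after death not free and no time-alive offset. The ICU heading in Appendix 4 likewise gives a workable convention for days after discharge. If a days-alive denominator was in fact meant, replacing it would exchange one defensible estimand for another, on which statisticians differ; the power results do not decide between them. Adding cancer to the Van Elteren strata brings no gain.

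The exposure is limited to one secondary outcome and, for the divisor, to the roughly 838 expected deaths, excluding those on support throughout. Survivors' scores and the primary mortality analysis do not depend on the divisor. Individual scores can differ widely (5.6% or 50%), but the size of any group-level gap rests on assumed death times, support durations and the share of deaths off support. The SAP's own appendices 1 and 2 are not in the text available for review; item 5 does not refer to them, so the conclusion rests on the protocol definitions.
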